6. STUDY PROCEDURES AND EVALUATIONS

Procedures to be performed during the study are summarized in Section 6.1 through Section 6.13, and scheduled procedures are indicated by visit in the Schedule of Assessments (Appendix A). More frequent assessments, as per Investigator or health-care-provider judgment, will be conducted if needed for management of AEs or per standard of care at each site.

Note: Week 12 and Week 36 planned visits for participants who roll over to this study from Study GBT440-042 will be for drug dispensing, collection of adverse events, and concomitant medications only.

Enrollment in this study, optimally, will occur on the same day as the last visit of the antecedent GBT voxelotor in which participants are eligible to participate in this open-label extension.

Note: The end-of treatment assessments performed upon completion of the antecedent study may serve as the Day 1 assessments for Study GBT440-038 and may be used as the baseline evaluations for Study GBT440-038. The investigational site is not required to repeat the assessments on Day 1 of participation in Study GBT440-038. As these end-of-treatment assessments were performed under the provisions of the antecedent study; it is not considered a protocol deviation if they are used for baseline assessments in Study GBT440-038 prior to obtaining informed consent in Study GBT440-038 since the assessments are covered under the antecedent study.

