6.10.2. Total Blood Volume

On-study blood volume collections will not exceed 2.4 mL/kg in any given 4-week period. Specific blood specimens (eg, exploratory measures) may be omitted at the discretion of the

^a For female participants of childbearing potential.

^b Only record on the CRF if the laboratory value is abnormal and considered clinically significant by the Investigator.

^c After implementation of Amendment 2 record bicarbonate values only; if the local laboratory only provides carbon dioxide values, do not record on the CRF.

Investigator, if warranted, such as in the context of blood loss associated with standard clinical care or bleeding events, or if otherwise deemed appropriate.

Due to total volume restrictions in pediatric research, assessments will be prioritized as indicated in Table 10.

Table 10: Priority of Study Assessments

Priority	Test
1	Hematology
2	Serum chemistry

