8.5. Handling of Missing Data

Data will be summarized as observed with no imputation for missing values, except for partially missing dates.

[figure not shown]

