11.7. Data Quality Assurance

All participant data relating to the study will be recorded on printed or electronic CRF unless transmitted to the Sponsor or designee electronically (eg, laboratory data). The Investigator is responsible for verifying that data entries are accurate and correct by physically or electronically signing the CRF.

Guidance on completion of CRFs will be provided in the CRF Completion Requirement document.

The Investigator must ensure that the CRFs are securely stored at the study site in encrypted electronic and/or paper form and are password-protected or secured in a locked room to prevent access by unauthorized third parties.

The Investigator must permit study-related monitoring, audits, IRB/EC review, and regulatory agency inspections and provide direct access to source records and documents. This verification may also occur after study completion. It is important that the Investigator(s) and their relevant personnel are available during the monitoring visits and possible audits or inspections and that sufficient time in devoted to the process.

Monitoring details describing strategy, including definition of study-critical data items and processes (eg, risk-based initiatives in operations and quality such as risk management and mitigation strategies and analytical risk-based monitoring), methods, responsibilities, and requirements, including handling of noncompliance issues and monitoring techniques (central, virtual, or on-site monitoring), are provided in the data management plan maintained and utilized by the Sponsor or designee.

The Sponsor or designee is responsible for the data management of this study, including quality checking of the data.

Records and documents, including signed ICFs, pertaining to the conduct of this study must be retained by the Investigator for 15 years after study completion unless local regulations or institutional policies require a longer retention period. No records may be destroyed during the retention period without the written approval of the sponsor. No records may be transferred to another location or party without written notification to the Sponsor. The

Investigator must ensure that the records continue to be stored securely for as long as they are maintained.

When participant data are to be deleted, the Investigator will ensure that all copies of such data are promptly and irrevocably deleted from all systems.

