Appendix A. SCHEDULE OF ASSESSMENTS

Study Day/Week	Treatment Period								EOS
	First 48 Weeks					After Week 48			+7 days c
	Day 1 a	Week 12 b ± 5 days	Week 24 ± 10 days	Week 36 b ± 10 days	Week 48 ± 10 days	Q12Wk ± 10 days	Q24 Wk ± 10 days	Q48 Wk ± 10 days	
Informed Consent/Assent	X								
Review Inclusion/Exclusion Criteria	X								
Medical History	X								
Weight and Height d	X		X		X			X	
Abbreviated Physical Examination ^e	X				X				
Vital Signs ^f	X	X	X	X	X		X	X	X
Adverse Events	X	X	X	X	X		X	X	X
Concomitant Medications	X	X	X	X	X		X	X	X
Hematology ^g	X	X	X	X	X		X	X	X
Serum Chemistry h	X		X		X			X	X
Urine Pregnancy Test i	X	X	X	X	X		X	X	X
Taste and Palatability Questionnaire with InClinic Dosing ^j	Performed on Day of Switch, and at the following two consecutive visits								
Transcranial Doppler k	Performed as standard of care								
Study Drug Dispensing and Accountability ¹	X	X	X	X	X	X	X	X	X

Abbreviations: CRF, case report form; EOS, End of Study; Q12Wk, every 12 weeks; Q24 Wk, every 24 weeks; Q48 Wk, every 48 weeks; TCD, transcranial Doppler.

Study Day/Week	Treatment Period					EOS			
	First 48 Weeks			After Week 48			+7 days ^c		
	Day 1 ^a	Week 12 b ± 5 days	Week 24 ± 10 days	Week 36 b ± 10 days	Week 48 ± 10 days	Q12Wk ± 10 days	Q24 Wk ± 10 days	Q48 Wk ± 10 days	

Voxelotor

GBT440-038

- a. Day 1 assessments will be performed prior to dosing. If any of the Day 1 assessments were performed at the last study visit in the originating (parent) clinical study, and the Day 1 visit occurs on the same date, the tests do not need to be repeated.
- b. Week 12 and Week 36 planned visits for participants who roll over to this study from Study GBT440-042 will be for drug dispensing, collection of adverse events and concomitant medications only.
- c. The EOS visit should be conducted 4 weeks (28 days) after the last dose of study drug (+7-day window).
- d. Height and weight will be collected only for participants < 18 years of age.
- e. Will include general appearance; examination of eyes, skin, cardiovascular system, and respiratory system; abdominal examination; and a symptom-directed examination.
- f. Heart rate and blood pressure will be measured after participant has rested for ≥ 5 minutes in the seated or supine position. If the first vital sign measurement is outside the normal range and deemed clinically significant, the measurement will be repeated within 5 minutes.

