- g. Will include the following: hematocrit, hemoglobin, mean corpuscular hemoglobin concentration, mean corpuscular volume, platelet count, red blood cell distribution width, reticulocytes (absolute and percent), and white blood cell count with differential.
- h. Will include the following: alanine aminotransferase, albumin, alkaline phosphatase, aspartate aminotransferase, bilirubin (total, direct, and indirect), blood urea nitrogen, creatinine, lactate dehydrogenase. Laboratory values for bicarbonate, calcium, chloride, glucose potassium, and sodium should only be recorded on the CRF if the laboratory value is abnormal and considered clinically significant by the Investigator).
- i. Will be performed for female participants of childbearing potential only. If the urine pregnancy test is positive, the result must be confirmed per local standard of care (eg, ultrasound or serum pregnancy test).
- j. Upon introduction of a new dosage form (either powder for oral suspension or dispersible tablets) or switch to higher dose (ie, modified dispersible tablet) to participants, a brief questionnaire will be administered to parents and/or children (aged ≥ 5 years) during the first visit when the transition is made and at the subsequent 2 scheduled visits.
- k. For all participants, results from TCD assessments performed as part of standard of care at each site will be recorded on the CRF.
- 1 Voxelotor will be dispensed in 12-week (~90-day) intervals with instruction to participants to return any used/unused bottles/stick packs to the clinic. At the Day 1 Visit, only study drug dispensing will be performed. At the EOS visit, only study drug accountability will be performed.

APPENDIX B. SCHEDULE OF ASSESSMENTS FOR SELECT SITES PARTICIPATING IN VOXELOTOR PLASMA AND WHOLE BLOOD PK COLLECTIONS UPON SWITCHING TO THE MODIFIED DOSE DISPERSIBLE TABLETS ^a

Study Day/Week	Day of Switch	14 Days Post-Switch	12 Weeks Post-Switch
PK Sample Collection (plasma and whole blood)	X	X	X
	(Predose)	(Predose)	(Predose)
Other Assessments	Per Scheduled Visit on Day of Switch (Appendix A) and must include Safety Assessments ^b Concomitant Medications Update	Safety Assessments ^b Concomitant Medications Update	Safety Assessments ^b Concomitant Medications Update
Taste and Palatability Questionnaire	X	X	X

Abbreviations: PK, pharmacokinetic.

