2. INTRODUCTION

The purpose of this statistical analysis plan (SAP) is to describe the planned analyses of data from Study GBT440-038 (C5341023).

Where applicable, the statistical analysis methods presented in this document will supersede the statistical analysis methods described in the study protocol.

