8.2.5 Clinical Laboratory Assessments

The following protocol-specified clinical laboratory findings will be summarized using descriptive statistics.

- 1. Hematology:
 - a. Hemoglobin (Hb)
 - b. Neutrophils (absolute and %)
 - c. Platelets
 - d. Reticulocyte count (percent and absolute reticulocyte)
 - e. White blood cells (WBCs)
- 2. Chemistry and Liver Function Tests:
 - a. Alkaline phosphatase
 - b. Alanine aminotransferase (ALT)
 - c. Aspartate aminotransferase (AST)
 - d. Potassium
 - e. Indirect bilirubin
 - f. Total bilirubin
 - g. Lactate dehydrogenase (LDH)
 - h. Serum Erythropoietin

Change from Day 1 and the percent change from Day 1 will be summarized for the above laboratory results. Analyte units will be converted to International System of Units (SI). The end-of-treatment assessments performed upon completion of the antecedent study may serve as the Day 1 assessments for Study GBT440-038.

Participant listings of laboratory data will include a separate listing for clinically significant laboratory results.

If indirect bilirubin is missing and direct and total bilirubin are collected, indirect can be calculated as:

 $Indirect \ Bilirubin = Total \ Bilirubin - Direct \ Bilirubin.$

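### SAP 8.2.5 plans potassium means and changes from Day 1, but the current protocol records potassium only when abnormal and clinically significant, so for visits under that rule the rows would describe selected values

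*SAP*

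**What the plan says.** **SAP.** Section 8.2.5 names the laboratory findings to be summarised descriptively. Potassium is item 2d under chemistry and liver function tests. The section then states: "Change from Day 1 and the percent change from Day 1 will be summarized for the above laboratory results". No analyte is exempted. Under SAP Section 8, a continuous variable is summarised by n, mean, SD, median, minimum and maximum.

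**Protocol.** Table 9 (Section 6.10) marks potassium with footnote b: "Only record on the CRF if the laboratory value is abnormal and considered clinically significant by the Investigator". Appendix A attaches footnote h to the row "Serum Chemistry h", scheduled at Day 1, Week 24, Week 48, every 48 weeks thereafter and EOS. That footnote repeats the rule and names potassium: "Laboratory values for bicarbonate, calcium, chloride, glucose potassium, and sodium should only be recorded on the CRF if the laboratory value is abnormal", with the same further condition of clinical significance. Section 6.10 has all tests done at local laboratories. On missing values, Section 8.5 says: "Data will be summarized as observed with no imputation for missing values, except for partially missing dates".

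**Day 1.** The protocol allows that end-of-treatment "assessments performed upon completion of the antecedent study may serve as the Day 1 assessments for Study GBT440-038". SAP 8.2.5 says the same.

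**The concern.** Values can be absent for reasons unrelated to their level, and an as-observed summary may then still be a fair description. Here the level itself decides whether the value is recorded: a normal potassium is not entered. A mean over what remains describes abnormal, clinically significant results, and no imputation or adjustment is planned that would bring the others back.

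The potassium rows would sit in the same table as ALT, LDH and hemoglobin, which are not subject to this rule. A reader could take them as the potassium level, and the movement in it, among treated participants. The printed n shows that few values contributed, but not that they were chosen for being abnormal.

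**Working it through.** The documents give no potassium figure, so there is no stated number to reproduce. The check is a comparison of texts, followed by an illustration of why the sign cannot be known.

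**1. Is potassium a special case?** SAP 8.2.5 has eight chemistry items. Potassium is the only one that carries footnote b in Table 9.

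**2. Does another provision supply the missing values?**
- SAP Section 2 says that "the statistical analysis methods presented in this document will supersede the statistical analysis methods described in the study protocol". This covers analysis methods and cannot restore values that were never recorded.
- Protocol 11.7 has data "recorded on printed or electronic CRF unless transmitted to the Sponsor or designee electronically (eg, laboratory data"). This is generic. Testing is local and no potassium feed is described.
- Protocol 8.5 rules out imputation.

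**3. What does the change from Day 1 contain?**
- Day 1 complete, for example from the antecedent study: only participants with a recorded follow-up value contribute. Their Day 1 values are therefore selected indirectly as well.
- Day 1 under the same rule: only participants recorded at both visits contribute.

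**4. Illustration.** Only the 600 comes from the documents (Protocol 3.1, an approximate upper limit). Assumptions: potassium normally distributed with SD 0.40 mmol/L and true mean 4.2 or 4.4, reference limits 3.5 and 5.1, correlation between Day 1 and follow-up of 0.3 or 0.6, no true change, and all 600 tested.

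At mean 4.2 the standardised limits are (3.5 − 4.2)/0.40 = −1.75 and (5.1 − 4.2)/0.40 = 2.25.

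- Share out of range: Φ(−1.75) + 1 − Φ(2.25) = 0.0401 + 0.0122 = 0.0523, and 600 × 0.0523 ≈ 31. For these inputs this is an upper bound on values recorded per visit, because clinical significance is also required.
- Shift in the mean if every out-of-range value were recorded: 0.40 × [φ(2.25) − φ(1.75)]/0.0523 = 0.40 × (0.0317 − 0.0863)/0.0523 ≈ −0.42. The row would show about 3.78 against a true 4.2.
- Shift if only high values were judged clinically significant: 0.40 × 0.0317/0.0122 ≈ +1.04.
- Apparent change with Day 1 complete = (1 − correlation) × shift.

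| True mean | Values recorded | Correlation 0.3 | Correlation 0.6 |
|---|---|---|---|
| 4.2 | all out of range | −0.29 | −0.17 |
| 4.4 | all out of range | +0.29 | +0.17 |
| 4.2 | high only | +0.73 | +0.42 |

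The true change is zero in every row. If Day 1 follows the CRF rule, the bivariate normal probability of being out of range at both visits gives about 3.5 (correlation 0.3) to 8.4 (correlation 0.6) participants of 600, again an upper bound for these inputs.

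The sign reverses with a 0.2 mmol/L change in the assumed mean, or with a different pattern of investigator judgement. These figures show the mechanism. They do not bound the real effect.

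**The case against.** **Little rides on these rows.** The endpoints are TEAEs and SAEs and the frequency of SCD-related complications. No tests are planned. Protocol 6.10 requires clinically significant laboratory abnormalities to be recorded as AEs, Section 7.2.3 uses hyperkalemia as its example, and SAP 8.2.5 already provides a separate listing of clinically significant results. A very small n beside a row would also make most readers cautious. All of this stands and limits the point to a minor correction. It does not make the summary meaningful.

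**Earlier visits may hold complete potassium data.** The documents do not say when footnote b took effect. Footnote c shows that a chemistry recording rule changed at Amendment 2, though it concerns bicarbonate. SAP 6.3 bases the final analysis on data from the whole study. Deleting item 2d outright could therefore discard a valid summary of fully recorded visits, and the listing of clinically significant results would not replace it. This stands, and the fix has to be conditional.

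**Readings that go too far.** A reader might infer that a potassium safety signal would be lost. The AE and listing requirements do not support that. A reader might also infer that the change sets unselected Day 1 values against selected follow-up values. A paired change does not do so, since only participants with a recorded follow-up value enter it.

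**Conclusion.** The two documents conflict, and nothing in either resolves it. For every visit under the current recording rule, the planned potassium mean, change and percent change would describe values selected by their own level. This follows from the text and needs none of the illustrative assumptions.

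The sign and size of the distortion cannot be derived: they depend on the potassium distribution, the local reference limits, investigators' judgement of clinical significance and the source of Day 1 values, none of which the documents give. It would be tempting to say that the rows are wrong for the whole study; the documents do not support that, because the recording rule in earlier protocol versions is unknown. The practical impact is minor, but the correction is worth making because it costs almost nothing.

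**What to change.** In SAP 8.2.5:

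1. Remove potassium from the descriptive, change and percent-change summaries for all visits under the abnormal-and-clinically-significant recording rule. State that these values are reported through the existing listing of clinically significant laboratory results. A count of participants affected is optional.
2. Have the sponsor confirm when the rule took effect. If potassium was recorded in full under an earlier protocol version, keep the summary for those visits only and label it so. Otherwise delete item 2d.
3. As separate housekeeping, delete serum erythropoietin (item 2h) or cite its data source. The section calls it protocol-specified, but it is absent from Table 9 and Appendix A. Protocol 6.10 does allow additional tests, so some values may exist.

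The cost is a few words in the SAP and one check of the amendment history. No new data collection and no protocol amendment are needed.

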8.2.6 Vital Signs and Physical Exam

Vital signs, including systolic and diastolic blood pressure, heart rate, height and weight will be summarized using descriptive statistics at each visit and time point. Change from Day 1 will also be summarized for each post-baseline visit.

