3.2. Duration of Study Participation and of the Study

Participants may receive study drug as long they continue to receive clinical benefit that outweighs risk as determined by the Investigator and/or until the participant has access to voxelotor from an alternative source (eg, through commercialization or a managed access program).

The study will end when the last participant's last visit occurs.

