3.4. Randomization and Unblinding

This is a nonrandomized, open-label study.

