6.5. Height and Weight

Height and weight will be collected for participants < 18 years of age at the time points indicated in the Schedule of Assessments (Appendix A).

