2.1 Study Overview

This multicenter, nonrandomized, global open-label extension (OLE) study is designed to assess the safety of, and sickle cell disease (SCD)-related complications with, long-term treatment with voxelotor in pediatric participants with SCD. The study will be conducted globally and will be available to eligible participants from Global Blood Therapeutics (GBT)/Pfizer-sponsored voxelotor clinical studies. Participants must have completed participation in their originating clinical study and must meet the entry criteria for this study to be eligible for enrollment.

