5. DEFINITIONS AND TERMINOLOGY

Study Day

Study Day is defined relative to initiation of treatment, i.e., Day 1. Thus, the study day of an event is calculated as:

$$Study Day = event date - Day 1 date + 1.$$

Study Visit

Study Visit is the nominal visit as recorded on the Case Report Form (CRF).

Change from Day 1

Change from Day 1 to follow-up visit will be calculated as Day 1 subtracted from the follow-up measurement for all assessments. Percent change from Day 1 values to post-Day 1 values will be calculated using the following formula where applicable:

Exposure to Study Drug

Duration of exposure to study drug is defined as the number of weeks from Day 1 to the last date of dosing of study drug. The derivation is as follows:

(Last dose date - First dose date
$$+ 1$$
)/7

Actual exposure to study drug is defined as the number of weeks from Day 1 to the last date of dosing of study drug which excludes days where treatment was entirely missed or intermittently stopped as recorded in the CRF. The derivation is as follows:

(Last dose date - First dose date - Number of days study drug was not taken +1)/7

Concomitant Medications

Concomitant medications are those medications taken on or after the initiation of study drug. This definition includes medications started prior to the initiation of study drug, but continuing concurrently with study drug.

Red blood cell (RBC) transfusions are collected on a separate CRF.

Treatment-Emergent Adverse Event

A TEAE is defined as an AE that emerges on or after initiation of study drug (having been absent pre-treatment), or an AE that existed pre-treatment and worsened on treatment (relative to the pre-treatment state) through 28 days after study drug discontinuation. AEs occurring on Day 1 are assumed to be treatment-emergent.

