8. STATISTICAL METHODS

Statistical analyses will be performed using SAS® Version 9.4 or higher.

Continuous variables will be descriptively summarized using number of participants (n), mean, standard deviation (SD), median, minimum, and maximum. Categorical variables will be descriptively summarized by presenting the number (frequency) and percentage in each category. All statistical analyses conducted will be descriptive and no formal statistical tests are planned.

Additionally, for the subset of participants receiving the modified dose of voxelotor in dispersible tablet in this study, separate summaries will be provided for selected CRF data (e.g., TEAEs).

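### Height and weight in participants under 18 are summarised only as raw values and raw change, which makes a moderate departure from expected growth hard to see in the planned tables

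*SAP*

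**What the plan says.** SAP 8.2.6 puts height and weight in the same sentence as blood pressure and heart rate: "height and weight will be summarized using descriptive statistics at each visit and time point". It adds: "Change from Day 1 will also be summarized for each post-baseline visit". SAP 5 defines that change as a plain difference for every variable: "Change from Day 1 to follow-up visit will be calculated as Day 1 subtracted from the follow-up measurement for all assessments". SAP 8 fixes the statistics: "Continuous variables will be descriptively summarized using number of participants (n), mean, standard deviation (SD), median, minimum, and maximum". SAP 8.1.2 also presents height, weight and BMI at Day 1, in raw units.

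Protocol 6.5 limits who is measured: "Height and weight will be collected for participants < 18 years of age". Appendix A schedules the measurements at Day 1, Weeks 24 and 48, and every 48 weeks after that. Treatment has no fixed end (Protocol 3.2): "Participants may receive study drug as long they continue to receive clinical benefit that outweighs risk". Protocol 3.4 states: "This is a nonrandomized, open-label study".

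Neither document mentions a z-score, percentile, growth velocity, growth reference or age-banded growth summary.

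**The concern.** A raw summary suits a variable that should stay roughly constant when nothing is wrong, such as blood pressure over a year. Height and weight in minors are not of that kind. The expected change is positive, depends on age and sex, and accumulates with time since Day 1. The number a reader needs is the gap between observed and expected growth, and the planned tables contain no expected value. A concurrent control would have supplied one, but there is none.

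The group behind each mean also changes. Participants stop contributing at 18. They may also leave once voxelotor is available elsewhere (Protocol 3.2). US approval starts at age 4 (Protocol 1.2), so departures could be related to age. Later means then mix growth with who is left.

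At stake is how informative one set of safety data will be in a study that the SAP describes as covering "long-term treatment with voxelotor in pediatric participants with SCD". Growth is not an endpoint, but the safety objective (Protocol 2, SAP 3) extends to further clinical measures beyond adverse events, laboratory tests and examinations.

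**Working it through.** **No figure to reproduce.** The study is descriptive, with no formal tests and no stated assumption about growth. The check has two parts: a reading of the texts, and an illustration whose growth inputs are all assumed.

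**1. Does any passage supply an age-adjusted growth summary?**
- SAP 5, 8, 8.1.2 and 8.2.6: raw values and simple differences only.
- Protocol 8: data may be summarised by antecedent study. This is optional, is not repeated in SAP 8.2.6, and does not standardise for age or sex.
- SAP 8: separate summaries of selected data for participants on the modified dispersible tablet. These are not age-standardised either.
- Protocol 5.1: the weight bands for participants under 12 run from 5 kg to 40 kg and above, and those aged 12 to 17 are measured too. The range of body size is therefore wide. The documents give no enrolled age distribution.

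**2. How far can age mix alone move the mean raw gain?**
Assumed height gain per 48 weeks in younger / middle / older children; mean gain = sum of (share × gain). Two assumed mixes are compared.

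| Assumed gains (cm) | Mix 50/35/15% | Mix 15/35/50% | Shift |
|---|---|---|---|
| 8 / 6 / 2 | 4 + 2.1 + 0.3 = 6.4 | 1.2 + 2.1 + 1.0 = 4.3 | 2.1 |
| 7 / 5.5 / 3 | 3.5 + 1.925 + 0.45 = 5.875 | 1.05 + 1.925 + 1.5 = 4.475 | 1.4 |
| 9 / 6 / 1 | 4.5 + 2.1 + 0.15 = 6.75 | 1.35 + 2.1 + 0.5 = 3.95 | 2.8 |

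The shift is 1.4 to 2.8 cm. The two mixes are deliberately far apart, so this is an outer range and not a forecast of drift within the study. With an assumed SD of 1 cm within each age band, the pooled SD of the gain is about 1.7 to 3.4 cm across the mixes tried, which included a near-equal one.

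**3. How large is a moderate growth effect on the same scale?**
Deficit in cm = loss in z × reference SD. Assume a loss of 0.1 to 0.3 z per 48 weeks and a reference SD of 4 to 7 cm:
- smallest: 0.1 × 4 = 0.4 cm
- middle: 0.2 × 5.5 = 1.1 cm
- largest: 0.3 × 7 = 2.1 cm

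The range of 0.4 to 2.1 cm overlaps the age-mix shift and lies mostly below it.

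**4. What would each table show?**
Observed raw change = expected gain − deficit. For expected gains of 4 to 7 cm:
- lowest: 4 − 2.1 = +1.9 cm
- middle: 5.5 − 1.1 = +4.4 cm
- highest: 7 − 0.4 = +6.6 cm

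The raw change is positive in every case. On a standardised scale, expected change under normal growth is about 0, so the middle case reads −0.2.

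The illustration covers height only. No calculation was made for weight, where the argument is qualitative.

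**The case against.** The strongest reply is that growth is not a study question. The endpoints are adverse events and SCD-related complications, the risk summary in Protocol 1.4 names no growth risk, and the only stated use of weight is in dosing participants under 12. This stands, and it limits the point to an improvement in a secondary safety summary.

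A reader might infer that the planned tables can show no growth effect at all, or that the mean must rise whatever the drug does. The documents do not support that. Weight loss or arrested growth would give a negative or flat change, and the minimum and maximum are reported. Nor are height and weight the only route. Protocol 7 has clinically significant changes in weight or examination findings recorded as adverse events, and the definition in Protocol 7.1.1 is broad enough for diagnosed growth faltering. These routes are coarse, and Protocol 7 does not list height, but they exist.

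A reader might also infer that a deficit of 1 cm per year is demonstrably masked by age mix. Against an assumed gain of 4 to 8 cm per year it is 1/8 = 12.5% to 1/4 = 25% of the gain, but those ratios say nothing about age mix. Change from Day 1 also removes each child's own starting size, so age mix enters that table only through growth rate. Any statement about masking is an illustration under assumed rates.

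Finally, z-scores do not identify a drug effect. There is no control, SCD itself may affect growth, and hydroxyurea and other SCD treatments are permitted (Protocol 5.7.2). Entrants had already received study drug in an earlier study (Protocol 4.1), so for those given voxelotor there, Day 1 is not a pre-exposure baseline. Ageing out and drop-out can bias mean z-score change too. All of this stands as a limit on interpretation, but none of it makes raw change a better summary of growth.

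**Conclusion.** The point holds as a low-cost improvement. As written, SAP 8.2.6 makes a moderate departure from expected growth hard to distinguish from normal growth and changing age mix. It does not hide gross effects, and it contradicts nothing else in the plan.

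That raw change lacks an expected value follows from the text alone: measurement only under 18, simple differences, open-ended follow-up and a single arm. The size rests wholly on assumed growth rates, age mixes and reference SDs. Under those, a loss of 0.1 to 0.3 z over 48 weeks equals 0.4 to 2.1 cm, against a possible age-mix shift of 1.4 to 2.8 cm.

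Because the analyses are descriptive, z-scores could be derived later without any cost in error control. The case for naming them now is that the growth reference is then chosen before the results are seen.

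**What to change.** In SAP 8.2.6, for participants under 18 and beside the raw values:
- add height, weight and BMI z-scores standardised for age and sex, from one named growth reference used at all sites;
- summarise change from Day 1 in z-score at the visits where Appendix A schedules height and weight;
- state that these show departure from a reference population, are not attributable to voxelotor without a control, and that Day 1 may not be a pre-exposure baseline.

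The cost is a set of derived variables. Age, sex, height and weight are already collected, so no new visit or measurement is needed. One check is required: SAP 8.1.2 gives age in years at Day 1, and z-scores need age more finely than completed years, so the sponsor should confirm that this is available. The small downside is that a single reference must be chosen for a global study, and it will fit some populations better than others.
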